*Ascertainment of illicit substance use/licit substance misuse:* Quicktest urine screening, which will include testing for buprenorphine (10 ng/mL), amphetamines (1000 ng/mL), barbiturates (300 ng/mL), benzodiazepines (300 ng/mL), cocaine (300 ng/mL), methadone (300 ng/mL), methamphetamines (1000 ng/mL), opiates (300 ng/mL), oxycodone (100 ng/mL), and THC (50 ng/mL), for a total of once weekly screening, will occur for CAP participants and those from other treatment programs. These urine toxicology screens will be performed by research staff. Participants will undergo urine toxicology screening at the time of each fetal monitoring session. Urine toxicology screening that is positive, i.e. representative of illicit substance use or licit substance misuse, at the time of fetal testing will result in cancellation of the fetal monitoring procedures for that day, with the exception of marijuana (see above).

*Ascertainment of other substances.* Alcohol is a well-known fetal teratogen, and chronic fetal exposure to alcohol will be excluded in the study populations. Any woman meeting DSM V or ASI criteria for alcohol use disorder will not be enrolled. We will also attempt to identify women using alcohol acutely; recent alcohol use will be verified with participant interview. Positive clinical screens for alcohol use will also be tracked via chart review. Women having evidence of or reporting recent alcohol use more than three times during the period of study enrollment will be removed from the protocol; however alcohol use emerged as a disenrollment criteria in only one participant in the prior study, likely due to our exclusion of alcohol use disordered participants based on ASI screening. In contrast to the low levels of alcohol use in our participants, cigarette smoking is routine, reflecting the larger CAP clientele: 88.5% use nicotine. Self-report data will be collected from each participant regarding the average number of cigarettes smoked per day upon enrollment and at each testing point. Women will be asked to refrain from smoking for 2 hours prior to each maternal-fetal recording. Nicotine withdrawal is unlikely in this time frame, and pregnant women are less likely to report any nicotine withdrawal in the first 24 hours of abstinence than non-pregnant women (Ussher, 2012).

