*Maternal psychiatric characteristics.* Approximately 75% of CAP clients report a current history of psychological problems at program intake, and more are diagnosed during treatment. All CAP clientele are referred for psychiatric evaluation after admission and near 40% receive medication, primarily selective serotonin reuptake inhibitors (SSRIs) prescribed for depression, the major Axis I disorder among CAP clients. However, many choose not to take these medications. Psychiatric diagnoses, medications prescribed and medications taking will be recorded for each subject.

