$\beta_3\text{peak} * \text{time} + \beta_4 \cdot \text{pX4\_p} + \varepsilon_{ij}$ , where  $\beta_3$  represents the rate of change in the difference in outcome between peak and trough over time. For Hypothesis 1C, we will fit a model where  $y_{ij} = \beta_0 + \beta_1\text{peak} + \beta_2\text{BN} + \beta_3\text{peak} * \text{BN} + \beta_4 \cdot \text{pX4\_p} + \varepsilon_{ij}$ , where  $\beta_3$  represents the between-treatment (BN-Methadone) or (BN-Buprenorphine) difference in peak-trough differences. Additionally, we will fit a model with a 3-way interaction between peak, time, and BN to determine if changes over time in peak-trough differences vary between BN and Buprenorphine.

For Hypothesis 2A, we will fit models separately for peak and trough measures where  $y_{ij} = \beta_0 + \beta_1\text{BN} + \beta_2 \cdot \text{pX2\_p} + \varepsilon_{ij}$  where  $\beta_1$  represents the difference in outcome between BN and Bup. We will also fit models where  $(y_{ij}) = \beta_0 + \beta_1\text{BN} + \beta_2\text{time} + \beta_3\text{BN} * \text{time} + \beta_4 \cdot \text{pX4\_p} + \varepsilon_{ij}$ , and  $\beta_3$  represents the difference in outcome trajectory over time between BN and Buprenorphine. For Hypothesis 2B, we will fit a model similar to 2A but only using data from 36 weeks to compare methadone and BN.

*Neonatal study:* For hypothesis 3A, we will use descriptive statistics to characterize NAS in BN-exposed infants, as measured by mean daily NAS scores on days 1-4 of life, highest NAS score, amount of medication (morphine sulfate, mg) required to treat NAS, number of days treated for NAS, and total days hospitalization. For hypothesis 3B, we will fit models of NAS severity (measured by Day 3 Finnegan scores, total medication used to treat NAS, total days of NAS treatment and total days of hospitalization), as a function of BN exposure (compared to methadone exposure), adjusting for maternal age, race, and non-opioid substance use. The models for hypothesis 3C will be analogous, but with buprenorphine exposure as the comparator. For hypothesis 3D, we will examine additional predictors of NAS severity including infant sex (Warren, 2015), daily and cumulative dose of BN, other medications including SSRIs (dosage and categorical), illicit drug use based on number of “dirty” urines and specific substance exposures, cigarette smoking (cigarettes per day and CO levels).

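### The NAS comparisons (3B, 3C) omit infant sex and SSRI use, which the plan records and names as NAS predictors, and do not say how smoking is entered

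*Combined protocol and SAP*

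**What the plan says.** The Neonatal study paragraph of Section 7b models NAS severity (Day 3 Finnegan score, total medication, days of treatment, days in hospital) "as a function of BN exposure (compared to methadone exposure), adjusting for maternal age, race, and non-opioid substance use". It then says: "The models for hypothesis 3C will be analogous, but with buprenorphine exposure as the comparator".

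For 3D the same paragraph continues: "we will examine additional predictors of NAS severity including infant sex". The list goes on to "other medications including SSRIs (dosage and categorical" and "cigarette smoking (cigarettes per day and CO levels". Section 2 labels 3D an exploratory sub-aim. Nothing there says that the B+N contrast is re-estimated with these terms in the model.

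All three variables are collected in this study:
- Infant sex comes from chart review (Postnatal protocol, Neonatal health status).
- Smoking is self-reported as "the average number of cigarettes smoked per day upon enrollment and at each testing point" (Section 4a, Ascertainment of other substances).
- For psychiatric medication, "Psychiatric diagnoses, medications prescribed and medications taking will be recorded for each subject" (Section 4a, Maternal psychiatric characteristics).

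The plan does not define non-opioid substance use or say how it is coded.

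**The concern.** Treatment is not randomised. B+N women are those who accept or request buprenorphine, plus stable patients of other providers. Methadone women come from the study clinic, and the only matching factor legible in Section 4a is route of administration, as a marker of OUD severity. The buprenorphine-only group dates from 2012-2016. Covariate adjustment therefore carries most of the weight in 3B and 3C.

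Section 4a chooses broad enrolment with later control of confounders, and names psychiatric comorbidity among the factors that may act independently on outcomes. The 3B and 3C models contain no psychiatric or psychiatric-medication term. Imbalance in SSRI use is plausible. All clients of the study clinic are referred for psychiatric evaluation and nearly 40% receive medication, mainly SSRIs. No such pathway is described for B+N women treated elsewhere.

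If SSRI use differs between groups and affects NAS, part of its effect is credited to the drug. In 3B this could create or mask the expected advantage of B+N. In 3C, where similarity is expected, it could hide a real difference or produce a false one.

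**Working it through.** **1. Reproduce the plan's figure.** Inputs from Section 7b, Computation of Power: 40 per group, alpha .05, power .80, effect size 0.63 SD. Two-sided testing is assumed because the plan does not state it.

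- n per group = 2(1.960 + 0.842)² / 0.63² = 39.6, so 40.
- Power at 40 per group: 80.4% (normal), 79.5% (noncentral t, 78 df). One-sided testing would give 87.5%, which does not match.
- Detectable effect: 0.626 SD (normal), 0.634 SD (t).

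The stated figure is an unadjusted two-group calculation, and it is correct.

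**2. Possible bias.** The documents give no covariate effect and no group imbalance, so every input here is assumed. Bias = imbalance × covariate effect on NAS, in SD.

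| Covariate | Assumed imbalance | Assumed effect | Bias |
|---|---|---|---|
| SSRI use | 10 to 30 percentage points | 0.2 to 0.5 SD | 0.10 × 0.2 = 0.02 to 0.30 × 0.5 = 0.15 SD |
| Cigarettes per day | 0.1 to 0.5 SD | 0.1 to 0.3 SD per SD | 0.1 × 0.1 = 0.01 to 0.5 × 0.3 = 0.15 SD |

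The upper end is 0.15 / 0.63 = 24% of the effect the study is sized on. With no true difference and 40 per group, a bias of 0.05, 0.10 or 0.15 SD raises the two-sided rejection rate from 5% to 5.6%, 7.3% or 10.2%. The cigarette row applies only if amount smoked is not already in the model.

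**3. Infant sex.** Maternal treatment should not alter it, so groups differ only by chance. With half of infants male (assumed), the standard error of the difference in proportions is √(2 × 0.25 / 40) = 0.112. The 95% range is therefore ±1.96 × 0.112, or about ±22 percentage points.

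**4. Precision.** Three terms are added (75 df). The detectable effect is 0.635 × √(1 − R²), where R² is the assumed share of residual NAS variance that they explain and they are unrelated to group.

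| R² | Detectable effect (SD) | Power at 0.63 SD |
|---|---|---|
| 0 | 0.635 | 79.4% |
| 5% | 0.619 | 81.4% |
| 10% | 0.602 | 83.4% |
| 15% | 0.585 | 85.5% |
| 20% | 0.568 | 87.5% |

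If the terms also explain a share v of group membership, the effect in the power formula is multiplied by √(1 − v). At v = 10%, power for R² of 0, 10 and 20% is 75.1%, 79.4% and 83.9%. Precision improves only when R² exceeds v.

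**5. Yes/no nicotine term.** If the sample resembles the clinic's clientele (88.5% users), non-users number about 0.115 × 80 = 9 of 80 infants' mothers. Almost all variation in smoking is then in the amount, which a yes/no term discards.

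**The case against.** **Smoking is not shown to be missing.** A reader might infer from the 3D list that cigarettes are left out of 3B and 3C. The text does not support that. Section 4a discusses nicotine under other substances, and it may belong to non-opioid substance use. 3D also lists illicit drug use and specific substance exposures, which overlap that adjuster, so appearing under 3D does not prove absence from 3B. Nor does the plan say that the term is coded yes/no. What stands is that the term and its coding are undefined.

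**Infant sex is not a confounder.** This is correct. Its omission supports an argument about precision and chance imbalance only.

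**The amounts are assumed and the precision gain may be nil.** Both are true. The bias argument supposes that the groups differ on the covariates, while the best precision figures suppose that they do not, so the two benefits should not be added together. Some confounding may already be removed through age, race and substance use, and bias could run either way.

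**Historical data.** The collection procedures describe the present study. Nothing shows that SSRI use or cigarettes per day exist in comparable form for 2012-2016, so a reader who takes the gap in 3C as avoidable goes beyond the documents.

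**General wording.** Section 4a promises control of confounders, and Section 7b says that the listed analyses are not exhaustive. Neither puts SSRI use or sex into the drug contrast. An open-ended list also leaves covariates to be chosen after results are seen.

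**SSRI measurement.** Psychiatric evaluation follows admission, and Section 4a says that many women do not take what is prescribed. Some women also join already stable on B+N. A yes/no at enrolment could misclassify exposure and would not be a clean pre-treatment value. This bears on how the term is defined and is no reason to leave it out.

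**Conclusion.** The point holds as a cheap improvement to the 3B and 3C models. SSRI use is a measured, plausible confounder that the plan itself names, and it is absent from the listed adjusters. Infant sex is absent too, at a cost in precision and chance imbalance. Smoking needs a definition and a scale.

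No stated figure is wrong, and the documents do not show that the B+N contrast is biased by any known amount. Under the assumed ranges, bias is about 0.01-0.15 SD per imbalanced covariate. The detectable effect moves from 0.63 to about 0.62-0.57 SD if the covariates are balanced and explain 5-20% of variance, and may not improve if they differ by group. The case is stronger for 3B, where the data are being collected, than for 3C, where they may not exist. It does not depend on changing the fetal or NNNS models.

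**What to change.** In Section 7b, Neonatal study:

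- **3B:** add infant sex and SSRI use to the adjusters. Define SSRI use as medication actually taken during pregnancy, and state the time window.
- **Non-opioid substance use:** list what it contains and how each part is coded. Enter smoking as continuous cigarettes per day, and state which of the recorded values is used.
- **3C:** before analysis, confirm whether the 2012-2016 cohort has SSRI use and cigarettes per day in comparable form. If so, use the same model as 3B. If not, state the limitation alongside the 3C result.
- **3D:** keep it as the exploratory look at predictors.

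The cost is SAP wording and about three degrees of freedom among 80 infants. 3B needs no new data. 3C needs a check of the historical records.

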### 2. Objectives (include all primary and secondary objectives)

*Aim 1:* Determine the acute effects of B+N and methadone exposure on the fetus by comparing fetal neurobehavior at times of peak and trough maternal B+N levels during the second half of gestation (24,28,32 and 36 weeks).

*Hypothesis 1a:* Fetal heart rate and motor activity patterns indicative of fetal well-being will be attenuated when maternal circulating B+N and methadone is at its peak as compared to trough concentration.

*Hypothesis 1b:* Differentials in fetal heart rate and motor activity patterns between peak and trough will increase over the course of gestation as neurobehavioral development becomes more organized.

*Hypothesis 1c:* The differential in fetal heart rate and motor activity patterns at peak and trough will be reduced in fetuses of B+N maintained mothers as compared to a matched cohort of methadone exposed fetuses, and will show either no difference or greater attenuation when compared to buprenorphine-only exposed fetuses.

*Aim 2:* Evaluate the development of the B+N-exposed fetus, and compare this with two other treatment exposures (a matched prospective methadone maintained group and a recent historical buprenorphine-only group).

*Hypothesis 2a.:* Fetal heart rate and motor activity patterns indicative of greater fetal well-being, and their developmental trajectory, will either not differ between B+N and buprenorphine-only groups at 24, 28, 32 and 36 weeks gestation, or they will be indicative of more optimal neurodevelopment. Separate comparisons will be made at both trough and peak levels to allow examination of both acute and chronic effects.

*Hypothesis 2b:* Fetuses of B+N maintained mothers, as compared to a matched cohort of methadone exposed fetuses, will exhibit fetal heart rate and motor activity patterns indicative of greater fetal well-being.

*Aim 3:* Determine the differential effects on the infant's NAS expression in B+N as compared to the other two treatment exposures (matched methadone exposed and historical buprenorphine exposed infants).

*Hypothesis 3a:* B+N-exposed infants will have mild NAS

*Hypothesis #3b:* B+N exposed infants will have less severe NAS symptomatology than methadone exposed infants, consist with current literature.

*Hypothesis #3c:* B+N exposed infants will have similar NAS severity relative to buprenorphine-only exposed infants.

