*Hypothesis #3d:* An additional exploratory subaim will seek to identify other maternal physiologic and/or fetal neurobehavioral markers that may predict NAS severity.

*Aim #4:* Will evaluate the longitudinal neurobehavioral developmental profile of B+N exposed infants up to 1 month of age. Infant neurobehavioral development will be compared to a matched cohort of methadone exposed and a historical cohort of buprenorphine only exposed infants.

*Hypothesis#4a:* B+N-exposed infants will evidence mild neurobehavioral alterations in the first month.

*Hypothesis #4b:* B+N-exposed, as compared to methadone-exposed infants will exhibit less severe neurobehavioral alterations.

*Hypothesis #4c:* The neurobehavioral functioning of the B+N and buprenorphine-only exposed infants will be similar.

*Aim #5:* Will evaluate concentrations of B+N in breast milk, maternal and infant plasma among breastfeeding women maintained on B+N.

*Hypothesis #5a-c:* B+N concentrations in a) maternal plasma, b) breast milk c) infant plasma will be low

*Hypothesis #5d:* B+N concentrations in breast milk, maternal plasma and infant plasma will be related to maternal dose of B+N.

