*Infant study:* For hypothesis 4A, we will use descriptive statistics to characterize BN-exposed infants' NNNS scores on each of 13 summary scales; based on previous work we will focus on habituation, arousal, excitability, and hypertonicity. We will fit a model to determine if NNNS scores change over time during the first month of life, and we will fit an additional model with an interaction between infant sex and time to determine if sex affects NNNS trajectories. For hypothesis 4B, we will fit models where  $\text{NNNS}_{ij} = \beta_0 + \beta_1\text{BN} + \beta_2 \cdot \text{pX2\_p} + \varepsilon_{ij}$ , and  $\beta_1$  represents the difference, across timepoints in the NNNS between BN and methadone exposed infants. We will then fit a model where  $\text{NNNS}_{ij} = \beta_0 + \beta_1\text{BN} + \beta_2\text{time} + \beta_3\text{BN} * \text{time} + \beta_4 \cdot \text{pX4\_p} + \varepsilon_{ij}$ , where  $\beta_3$  represents the difference in NNNS trajectories over time between BN and methadone-exposed infants. For hypothesis 4C, we will fit analogous models to 4B, but with buprenorphine-exposed infants as the comparator. These models will be adjusted for maternal age, race, dosing, and other substance use.

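### Hypotheses that B+N resembles buprenorphine-only (3c, 4c and the no-difference parts of 2a and 1c) have only difference models and difference power, with no rule for what would support similarity

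*Combined protocol and SAP*

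**What the plan says.** Section 2 (Objectives) makes four predictions against the historical buprenorphine-only group:

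- 3c: "B+N exposed infants will have similar NAS severity relative to buprenorphine-only exposed infants".
- 4c: "The neurobehavioral functioning of the B+N and buprenorphine-only exposed infants will be similar".
- 2a: fetal patterns and trajectories "will either not differ between B+N and buprenorphine-only groups at 24, 28, 32 and 36 weeks gestation", or will be more optimal.
- 1c: the peak-trough differential "will show either no difference or greater attenuation when compared to buprenorphine-only exposed fetuses".

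Section 7b gives the models. For 2a, the main coefficient "represents the difference in outcome between BN and Bup", and the interaction coefficient "represents the difference in outcome trajectory over time between BN and Buprenorphine". For 1c, the coefficient of interest is the between-treatment difference in peak-trough differences. For 3c, "The models for hypothesis 3C will be analogous, but with buprenorphine exposure as the comparator", where the model being copied is that of 3b, the less-severe-than-methadone hypothesis. For 4c: "For hypothesis 4C, we will fit analogous models to 4B, but with buprenorphine-exposed infants as the comparator".

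The Computation of Power text in section 7b gives, at 80% power and alpha .05, detectable differences of 4.23 (SD 6.68), 4.12 (SD 6.49), .63 SD and .44 (SD 0.70) for hypotheses 1 to 4. It also gives simulated trajectory differences of .35 and .32 per week and .04 per day. Nothing in the document gives a margin, a confidence interval rule or a definition of similar.

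**The concern.** A model built to detect a difference, with power computed for a difference, answers a different question from a hypothesis of similarity. If the plan is followed as written, the only test outcome that fits 3c, 4c or the no-difference part of 2a is failure to reach significance. Small or noisy data make that outcome more likely.

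This matters because B+N against buprenorphine-only is the comparison that bears on adding naloxone. Section 9 (Benefits) rests the study on B+N being no more harmful to offspring than buprenorphine, and says that confirming the hypotheses will benefit care. Without a rule fixed beforehand, an imprecise estimate from 40 per group could be taken as that confirmation.

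**Working it through.** **Inputs.** 40 B+N completers (section 4a); 40 buprenorphine-only, alpha .05, 80% power and the detectable differences (section 7b). Sidedness is not stated; two-sided reproduces the figures. The calculations are unadjusted.

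**1. The plan's own figures.** In SD units: 4.23/6.68 = 0.633; 4.12/6.49 = 0.635; .63; .44/.70 = 0.629. A two-sample t test with 40 per group and two-sided .05 has 80% power at 0.634 SD. The stated power therefore reproduces, and it is power for a difference.

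**2. One roughly normal value per infant (3c, for example the Day 3 Finnegan score).**
- SE = sqrt(2/40) = 0.2236 SD, with 78 degrees of freedom and critical t = 1.991.
- 95% CI half-width = 1.991 × 0.2236 = 0.445 SD.
- Probability of a non-significant result, from the non-central t:

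| True difference (SD) | Non-centrality | P(non-significant) |
|---|---|---|
| 0.3 | 0.3/0.2236 = 1.34 | 73.7% |
| 0.5 | 0.5/0.2236 = 2.24 | 40.2% |

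**3. What the sample could show about similarity if the true difference were zero.** The 90% CI half-width is 0.372 SD. To lie inside ±0.5 SD, the estimate must be within 0.5 − 0.372 = 0.128 SD of zero, and 0.128/0.2236 = 0.57 standard errors. The probability is 43% (43.3% when integrated over the variance estimate). It reaches 80% only at a margin near 0.66 SD. These margins are illustrative, since the documents give none.

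**4. Means over visits (2a).** Multiply the half-width by f = sqrt((1+(m−1)ρ)/m) for m visits. The documents give no between-visit correlation, so ρ is assumed to be 0.3 to 0.7.

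| Visits per woman | f | Half-width (SD) | On SD 6.49 |
|---|---|---|---|
| 4 | 0.689–0.880 | 0.31–0.39 | 2.0–2.5 |
| 2 | 0.806–0.922 | 0.36–0.41 | 2.3–2.7 |
| 1 | 1 | 0.45 | 2.9 |

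The four-visit row holds only if every woman completes all four. Section 4b allows entry up to 34 weeks with fewer visits for later entrants, and section 4a cancels sessions after a positive urine screen, with an exception for marijuana. Fewer visits are therefore likely. For 4c, three complete NNNS visits give f = 0.730–0.894 and a half-width of 0.33–0.40 SD under the same assumption.

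**5. Trajectory (2a).** If powered means 80% at two-sided .05, then SE = .32/(1.960 + 0.842) = 0.114 per week. The half-width is 1.960 × 0.114 = 0.22 per week, or 0.224 × 12 = 2.7 over weeks 24 to 36. A true difference of half the detectable size (.16 per week) would be non-significant 71% of the time.

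**Not covered.** The 1c interaction (the plan does not say whether SD 6.68 is that of the peak-trough difference); total medication and treatment days, which are zero for untreated infants; hospital days; and covariate adjustment.

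**The case against.** The strongest reply is that nowhere does the plan say a non-significant result will be called similar. The planned coefficients are B+N minus buprenorphine estimates, and confidence intervals come with them. Section 7b also says that its list of analyses is not exhaustive. This stands in part. A reader might infer that the sponsor intends to equate non-significance with similarity, but the documents state no such rule. The finding is the absence of any rule. A general remark that more analyses may follow does not supply a criterion for a named hypothesis.

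Three stronger readings should also be resisted.

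- *The power calculation is wrong.* It reproduces. It simply does not apply to similarity.
- *The 4c trajectory is too imprecise to be useful, with an interval wider than one SD.* Scaling the stated .04 per day over days 3 to 30 and comparing the result with SD 0.70 would suggest this. The comparison is not supported: .04 is for the arousal subscale, from a simulation whose inputs are not given, while 0.70 is quoted for NNNS subscales generally. The two do not fit together. With SD 0.70, visits on days 3, 14 and 30, random intercepts and correlation 0.3–0.7, the detectable slope would be about 0.019–0.013 per day and the half-width 0.36–0.24 points over that period.
- *1c is a not-worse hypothesis.* Section 2 links attenuation to reduced well-being patterns at peak in 1a, but expects a reduced peak-trough differential against methadone in 1c. Whether greater attenuation is favourable is not clear, so no direction can be assigned.

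**Conclusion.** The concern holds for 3c, 4c and the no-difference part of 2a: neither the models nor the power support a conclusion of similarity, and no criterion is given. For 2a, a significant result favouring B+N would fit its other branch; the gap is in the no-difference branch. The buprenorphine-only part of 1c has the same gap, with its direction unresolved and its size not estimated.

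The main size statement is step 2: a non-significant result is the likelier outcome at a true 0.3 SD and still common at 0.5 SD. It rests on 40 per group, one roughly normal value per infant, two-sided .05 and no covariate adjustment. Averaging over visits narrows the intervals, by an amount that depends on an assumed correlation and on how many visits are completed. The models can stay and the data remain usable. This should be fixed, but it does not invalidate the design.

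**What to change.** In section 7b (Fetal, Neonatal and Infant studies), add:

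> For 1c, 2a, 3c and 4c versus buprenorphine-only we will report the adjusted B+N minus buprenorphine estimate with its 95% CI, for mean and trajectory terms where fitted. A non-significant difference will not be taken as evidence of similarity.

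Under Computation of Power, state that the figures are for detecting differences and do not apply to similarity.

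In section 2, reword 3c, 4c and the no-difference parts of 1c and 2a as estimation with no similarity verdict. Bring the section 9 text on equal harm and on confirming the hypotheses into line.

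Only if the sponsor wants to claim similar or not worse should it first name the variable, a justified margin, the unfavourable direction (after clarifying 1c) and the CI level. The figures in step 3 of the working describe what this sample can show; they do not set a margin.

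The cost is wording in sections 2, 7b and 9, with intervals read from models already planned and no added participants. Margins would cost more, because section 7a leaves the number of NNNS scales to exploratory analysis and a main variable would have to be chosen first. The downside is that some similarity claims will be reported as inconclusive or as estimates only.
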